3 OVERALL DESIGN AND PLAN OF THE STUDY

3.1 Summary of Study Design

This is a multicentre, randomised, double-blind, Phase II, parallel group comparison study of the efficacy and safety of FP-1201-lyo compared to placebo in patients surviving emergency open surgery for an infra-renal ruptured abdominal aortic aneurysm. Both treatment groups will receive standard supportive care.

With an estimated screening failure rate of approximately 15%, maximum of 180 patients will be consented and entered into the study in order to randomise and initiate treatment of 152 patients. The sample size calculations will be re-evaluated after the first interim analysis has been performed.

The study design incorporates an Independent Data Monitoring Committee (IDMC) that will review safety data retrieved for interim analysis (i.e. Adverse Events [AE] and Serious Adverse Events [SAE]). Details of the IDMC are given in Section 9.8.

[figure not shown]
Patients will receive 10 µg FP-1201-lyo or placebo intravenously as a bolus injection once every 24 hours. The maximum duration of treatment will be 6 days. Treatment may be discontinued before 6 days if the patient's condition improves beyond the need for ICU treatment and if, in the opinion of the Investigator, the patient would likely not benefit from continuation of treatment.

A schedule for the tests and assessments to be conducted during this study is found in the Tables 5-8.

The study objectives and outcome measures to be used in this study are described in Sections 2 and 6.

The study design is summarised below in Figure 1.

Figure 1: Flow Diagram of Study Design

3.2 **Criteria for the Study assessments**

3.2.1 **Primary Efficacy Endpoint:**

- All-cause mortality at D30

Secondary Efficacy Endpoints:

- All-cause mortality at D90 (3 months)
- Number of ventilator free days (VFDs) at D30
- Number of days receiving hemodialysis at D30 and D90
- Number of organ failure free days up to D30 by means of the SOFA score
- Prevalence of abdominal compartment syndrome, i.e. intra-abdominal pressure (IAP) between study groups
- Neutralizing antibodies against IFN beta-1a (NAbs) in whole blood samples up to D30
- Disability at D90 (3 months) by modified ranking scale.

3.2.2 **Safety**

- Clinically significant treatment emergent adverse events (TEAEs) up to D30 from vital signs data, laboratory data, physical examinations and spontaneous reporting when conscious

3.2.3 **Pharmacoeconomics assessments**

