6.2.6 Days in hospital and/or other health care unit

The length of a patient's hospital stay will be assessed by:

- the number of days the patient stayed in hospital at D30 and D90
- the number of days the patient stayed at another primary or rehabilitating health care unit after hospital discharge at D30 and D90.

6.2.7 *Days on haemodialysis*

The number of days on haemodialysis will be assessed at D30 and D90. Haemodialysis at D90 is considered permanent.

6.2.8 *Prevalence of compartment syndrome as measured by intra-abdominal pressure (IAP)*

Intra-abdominal pressure (IAP) is routinely measured during ICU stay via urine bladder catheter. IAP is recorded daily and a comparison of IAP between study groups is made.

6.3 **Safety Variables**

6.3.1 *Adverse Events*

6.3.1.1 *Collection of Adverse Events*

It is the responsibility of the Investigator to collect all AEs (both serious and non-serious) derived by observation, by spontaneous unsolicited reports of patients, and, where appropriate, by routine open questioning, e.g., “How have you felt since I last saw you?”

6.3.1.2 *Definitions*

Definitions of AEs and SAEs and their documentation and reporting within this study follow International Conference on Harmonisation (ICH) Good Clinical Practice, European Union, and national regulations and requirements (Clinical safety data management 1994).

An AE is defined as any untoward medical occurrence that occurs in a patient or clinical investigation subject administered a pharmaceutical product, and which does not necessarily have to have a causal relationship with this treatment. An AE can therefore be any unfavourable and unintended sign (including an abnormal laboratory finding), symptom or disease temporally associated with the use of an investigational product, whether or not it is considered related to the product.

All AEs up to D30 are collected. All AEs up to D30, which lead to death, are reported as SAEs. However, all deaths up to D90 will be reported as SAEs. Concomitant illnesses, which existed before entry into the study, will not be considered AEs unless there is any deterioration from baseline that is considered clinically relevant or significant during treatment or follow-up period until D30 or discharge from ICU. All AEs must be documented, regardless of the source of identification (e.g., physical examination, laboratory assessment, ECG, reported by patient).

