- + Study specific procedures must be performed after informed consent for the study is obtained. If ICU standard procedures are in line with the study procedures and if the timing of RAAA diagnosis, consent, operative treatment and dosing preclude repetition of procedures for the purposes of the study, then standard patient care test results may be used for screening even prior to obtaining consent
- ++ Evaluation of the value before surgery
- ∇ Study medication, FP-1201-lyo or placebo, is administered as a bolus intravenous injection, followed by a 5 ml flush of sterile saline. On D0, the first dose of study

medication is administered at 0h. Subsequent doses from D1 to D5 are administered every 24 hours \pm 1 hour.

- ❖ SOFA scores are assessed daily in the ICU from D0 post-dose to D30, as applicable by standard clinical treatment at that point. (Therefore, if a patient does not have an arterial line, no arterial blood sampling should be taken.)

** Only for females under age of 60 years.

Table 6: Flow Chart for the Short Term and Mid Term Follow-up Periods

ASSESSMENTS	Short Term Follow-Up*				D90 (+14 days) 3 months
	D6	D9**	D13**	D30	
Check whether patient is in the ICU	X	X	X	X	
Check whether patient is on ventilation	X	X	X	X	
Check whether patient is on organ support (hemodialysis)	X	X	X	X	X
SOFA Scoring ❖ (worst daily value should be used)	X	X	X	X	
Ventilator Free Days (VFDs)				X	
Physical Examination	X	X	X	X	
Vital Signs; Temp, BP, HR (closest to 8am)	X	X	X	X	
Blood Biochemistry	X	X	X	X	
Haematology	X	X	X	X	
Intra-abdominal pressure (IAP) (closest to 8am)	X	X	X		
MxA, CD73 and PIM	X 22h \pm 2h since Dose 6	X	X		
NAbs				X D30 \pm 5D	
Mortality (reason/diagnosis of death)				X	X
Concomitant Medications/Therapies	←-----X-----→				
AE Recording	←-----X-----→				
Deaths Recording		X			X
mRS					X

KEY:

- * Assessments prior to D30 are only performed if patient is still hospitalised in the same hospital initially operated. If the patient is moved to a different hospital, assessments will not be done. If study treatment is terminated early by Investigator decision due to patient improvement, the study assessment schedule should be followed as normal.

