- Blood pregnancy test if relevant (only for females under age of 60 years)
- Haematology (refer to Section 6.3.2 for specific haematology variables)
- Pharmacodynamics (PD): MxA sample for central testing within 1 hr pre-dose
- Secondary efficacy: Neutralizing antibodies IFN-beta (NABs) sample within 1 hr pre-dose
- Tentative Disease Specific Marker CD73 and Potential Inflammatory Marker (PIM) samples for central testing within 1 hr pre-dose

- Recording of concomitant medications and therapies
- Collection of Adverse Events from this time point onward: All Adverse Events and Serious Adverse Events will be collected from the time of informed consent signature and throughout the study until the last follow-up visit.
- Recording of major surgical outcomes affecting patient
 - open abdomen (yes/no)
 - left renal vein ligated (yes/no)
 - Clamping time above the renal arteries

In practice, at arrival at the ICU standard artery-astrup analysis for haematology and biochemistry are performed. Tubes for disease and medication specific markers are drawn at the same time and stored in the ICU. After sampling, the study medication is begun. The study medication is also stored in the ICU.

7.5 TREATMENT PERIOD (D0 to D5) and SHORT TERM follow-up period (D6 to D30): STUDY MEDICATION ADMINISTRATION, PATIENT CARE, AND ASSESSMENTS

The study treatment period comprises D0 to D5 inclusive. Most procedures and assessments to be performed on D0 are pre-dose (with the exception of recording of SOFA scoring, concomitant medications and therapies and AE reporting) and they are detailed in Section 7.4.2.2.

The procedures and assessments to be performed on D0 from the time of study medication administration to D5 are detailed in Section 7.5.1.

The procedures and assessments to be performed in the short-term follow-up period are detailed in Section 7.5.2.

Assessments from D0 and prior to D30 are only performed if the patient is hospitalised in the operating hospital (where the patient was operated and recruited in the trial).

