- MxA, CD73 and PIM samples for central testing within the timeframe of 22 hours \pm 2 hours after the previous day's administration of study medication, however before the next study drug dose
- Recording of concomitant medications and therapies
- AE reporting

Note: Where a patient's condition precludes an assessment taking place as scheduled, the assessment should be performed within \pm 2 hours of the scheduled time and, if this is not possible, the assessment will not be performed and the reason for non-performance will be recorded. However, every effort must be made to perform all assessments.

Each day on D0 to D5 inclusive, the study medication, FP-1201-lyo or placebo, is administered as a bolus intravenous injection **24 hours \pm 1 hour after the previous day's administration of study medication** and the following study assessments and procedures are performed **post study medication administration:**

- Recording of concomitant medications and therapies
- AE reporting commences after obtaining the informed consent.

7.5.2 **Schedule of assessments for the short-term follow-up period (D6 to D30)**

Daily assessments are performed up to D30 if the study patient is still hospitalized in the same hospital where initially operated. If the patient is moved to a different hospital (or home), assessments will not be done. All assessments should be performed at the same time of a day as the D6 assessments were performed. **Note:**

Where the patient's condition precludes an assessment taking place as scheduled, the assessment should be performed within ± 2 hours of the scheduled time, and if this is not possible, then the assessment will not be performed and the reason for non-performance will be recorded. However, every effort must be made to perform all assessments.

The following study assessments and procedures will be performed as below from D6 to D30 (refer to flow charts in Table 6):

- Check if patient is on ventilation (refer to VFD definition in Section 6.2.3)
Patients still on positive pressure ventilation who are transferred to another hospital or healthcare facility prior to D30 will be followed up to assess the VFD outcome at D30.
- Check if patient is in the ICU
Patients still on ICU who are transferred to another hospital or healthcare ICU facility prior to D30 will be followed up to assess the days on ICU at D30.
- Check if patient is on organ support

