13.1 Adverse events

All recorded adverse events will be coded according to the Medical Dictionary for Regulatory Activities (MedDRA). Treatment emergent adverse event (TEAE) is defined as an AE that begins or worsens in severity after at least one dose of study drug has been administered. Non-treatment emergent AEs are listed only.

TEAEs will be summarized using frequency and subject based tables. TEAEs will be tabulated by treatment group, system organ class (SOC), preferred term (PT), causality and severity. For analysis purposes, each subject will also be categorized by the maximum severity reported for a given TEAE and these will be tabulated by maximum severity. TEAEs will be summarized separately for treatment period (D1-D5) and short-term follow-up period (D6-D30). TEAEs are not collected, and therefore not reported, during the mid-term follow-up.

Serious adverse events (SAEs) and AEs leading to discontinuation will be summarized by treatment groups. All deaths up to D90 are reported as SAEs.

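### AE reporting falls under a rule that suspends assessments once the patient leaves the operating hospital, while the safety section requires all AEs to D30; no passage says how new AEs are sought after leaving

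*Protocol*

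**What the plan says.** **Safety endpoint and collection duty.** Protocol 3.2.2 defines the endpoint as "Clinically significant treatment emergent adverse events (TEAEs) up to D30 from vital signs data, laboratory data, physical examinations and spontaneous reporting when conscious". Section 6.3.1.2 states: "All AEs up to D30 are collected". Section 6.3.1.4 starts AE reporting at consent, and 6.3.1.5 requires every SAE from consent to D30, plus all deaths to D90. None of these sections sets a condition on where the patient is.

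**Location rule.** Section 7.5 says "Assessments from D0 and prior to D30 are only performed if the patient is hospitalised in the operating hospital". Section 7.5.2 says "If the patient is moved to a different hospital (or home), assessments will not be done", and the list that follows ends with AE reporting. The keys to Tables 5 and 6, both of which have an AE row, say "Assessments prior to D30 are only performed if patient is still hospitalised in the same hospital initially operated". SAP Appendix 19.2 reproduces this key.

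**Exceptions to the rule.** Sections 7.5.2 and 7.6.1 follow transferred patients to D30 for ventilator-free days and ICU days. Section 7.6.1 also follows AEs already ongoing at discharge, until they resolve or D30. It does not mention AEs that begin later.

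**D30 contact.** Section 6.3.2 gives the neutralising-antibody sample as the only reason for a laboratory visit after discharge. Section 7.6.1 invites the patient for that sample and for further, unlisted D30 assessments.

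**Other end points for AE collection.** Worsening of a pre-existing illness counts "during treatment or follow-up period until D30 or discharge from ICU" (6.3.1.2). Section 7.4.2.2 has AEs and SAEs "collected from the time of informed consent signature and throughout the study until the last follow-up visit".

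**Analysis.** SAP 13.1 tabulates TEAEs by events and by subjects, separately for D1–D5 and D6–D30, in all treated patients (FAS-S). It makes no allowance for time observed.

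**The concern.** A site that follows 7.5.2 as written can reasonably stop AE reporting on the day of transfer. The exceptions for ventilator and ICU days make this reading easier, because they show that the authors considered transferred patients and did not list AEs. Section 5.7 adds to the contrast: discharged patients must be told to report additional medication up to D30, but no similar instruction covers new symptoms or events.

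Three of the endpoint's four named sources (vital signs, laboratory data and physical examination) are not scheduled between leaving and D30. The fourth, spontaneous reporting, depends on someone being told. An event on D15 in a patient transferred on D10 may be picked up at D30 or may not, and practice may vary by site.

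What is at stake is the between-arm comparison of D6–D30 TEAEs. The denominator is every treated patient, but the period of active observation ends at a point that treatment could itself influence.

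**Working it through.** The plan gives no figure on this point, so there is none to reproduce. The check has two parts.

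**1. The passages side by side**

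- Must AEs be collected to D30 after the patient leaves? Yes under 6.3.1.2, 6.3.1.4 and 6.3.1.5. No under a literal reading of 7.5, 7.5.2 and the Table 5/6 keys, for the time before D30.
- Is there a contact at D30? Yes (7, 7.6.1), though 6.3.2 limits the visit to the antibody sample.
- Is an enquiry for new AEs since leaving specified, whether at D30, by phone or from the receiving hospital? No passage does so.
- Does the analysis allow for unequal observation? No (SAP 13.1).

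**2. How much it could matter**

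Input from the documents: the D6–D30 window is 30 − 5 = 25 days.

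Assumptions, none of them in the documents:
- true D6–D30 incidence *p*, the same in both arms, with a constant hazard
- day of leaving *L*
- full capture in the operating hospital
- a share *c* of AEs captured after leaving

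Formulas: *h* = −ln(1 − *p*)/25, and recorded incidence = 1 − exp(−*h* × [(*L* − 5) + *c* × (30 − *L*)]).

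For *p* = 0.60, *h* = 0.9163/25 = 0.03665 per day. With one arm leaving on D10 and the other on D15, fully observed time is 5 v 10 days.

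| Off-site capture *c* | Effective days, D10 v D15 | Recorded incidence | Gap (points) |
|---|---|---|---|
| 0 | 5 v 10 | 16.7% v 30.7% | 13.9 |
| 0.5 | 15 v 17.5 | 42.3% v 47.3% | 5.1 |
| 0.8 | 21 v 22 | 53.7% v 55.4% | 1.7 |
| 1 | 25 v 25 | 60% v 60% | 0 |

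Gaps are taken from unrounded values.

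For the same days of leaving, the gap at true incidence 40%, 60% and 80% is:
- *c* = 0: 8.8, 13.9 and 19.9 points
- *c* = 0.5: 3.7, 5.1 and 5.7 points
- *c* = 0.8: 1.3, 1.7 and 1.6 points

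Widening the contrast from D10 v D13 up to D10 v D20, over the same three incidences, the gap runs from 5.4 to 34.4 points at *c* = 0, from 2.2 to 10.5 at *c* = 0.5, and from 0.8 to 3.3 at *c* = 0.8. At *c* = 1 it is always zero. The result therefore turns on off-site capture, the one quantity the protocol leaves open.

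**The case against.** The strongest reply is that section 6.3.1 governs safety and sets no location limit, so 7.5.2 should be read as relieving sites of daily in-person procedures and not as cancelling a separate safety duty. Several passages support this. The location rule covers only the time before D30, so the D30 assessment lies outside it. Table 6 draws AE recording as a continuous arrow. Section 6.3.1.1 provides for open questioning about how the patient has felt since last seen, and asked at D30 that question would cover the whole interval. Deaths are reported to D90 in any case.

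Much of this stands. A reader might infer that AE collection simply ends on transfer; the documents do not support that, because the duty to D30 is stated more than once and a D30 contact is planned. What remains is that two sets of instructions conflict, no passage says which prevails, and none turns the general duty into a method for finding new off-site events.

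A reader might also infer that the tables favour the arm that leaves sooner. The documents do not support that either. They give no length of stay by arm, and death also shortens observation. Under the plan's own assumption of 37% v 15% D30 mortality (8.2), more placebo patients would have their observation cut short by death, which pulls the other way.

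The constant hazard is also open to challenge. Section 5.8 expects few drug-related effects after the treatment period, and patients who go home are likely to be the recovering ones. Both would reduce the gaps shown above. D1–D5 TEAEs are tabulated separately and are less exposed.

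**Conclusion.** The point holds as an internal contradiction with a missing procedure. Sections 7.5, 7.5.2 and the Table 5/6 keys suspend a list that includes AE reporting. Section 6.3.1 requires AEs and SAEs to D30 regardless of location. The link between them, a defined enquiry for new AEs after leaving, is absent.

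Bias in the D6–D30 tables needs two conditions: incomplete off-site capture, and observed time that differs by arm. The documents establish neither, and they do not settle the direction. The size is correspondingly uncertain: about 14, 5 or 0 points in the 60% example at no, half or full capture. These figures are illustrations that rest on the assumed incidence, days of leaving and constant hazard; they are not estimates for this trial.

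It is more than a matter of drafting, because a site complying with 7.5.2 would under-record TEAEs after transfer and the SAP tables would not reveal it. It should be corrected.

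**What to change.** **Protocol**
- Exempt AE and SAE recording from the same-hospital rule in 7.5, 7.5.2 and the keys to Tables 5 and 6.
- State that the D30 contact, by visit or phone, includes an enquiry for new AEs and SAEs since leaving. For patients who were transferred or have died, add receiving-hospital records. Follow-up of transferred patients to D30 is already required for ventilator and ICU days.
- Reconcile 6.3.2 with 7.6.1 on what the D30 visit covers.
- Reconcile the ICU-discharge cut-off in 6.3.1.2 and the last-visit wording in 7.4.2.2 with the D30 window.

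**SAP**
- SAP section 2 records that the study was discontinued after the first interim analysis, so protocol wording may no longer change what was collected. For data in hand, report D6–D30 TEAEs alongside days observed in the operating hospital by arm, with observation ended by departure, death or D30. The discharge-day evaluation in Table 7 and the planned listings of deaths (16.2.13) and length of stay (16.2.17) should supply most of what is needed.

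**Cost.** Some protocol wording, one structured question at a contact already planned, and one additional summary in the safety tables. The downside is that non-serious AEs after transfer will be recalled less precisely than those seen on the ward.

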7.6 Discharge

7.6.1 Discharge prior to D30

If a patient is discharged from the operating hospital prior to D30 and not discontinued, a complete **final evaluation** should be made **at the day of discharge** as described below (refer to Table 7):

- Check if patient is on ventilation (refer to VFD definition in Section 6.2.3)
All patients, whether still on or already off positive pressure ventilation, who are transferred to another hospital or healthcare facility prior to D30 will be followed up to assess the VFD outcome at D30.
- Check if patient is in the ICU
Patients that are transferred to another hospital or healthcare ICU facility prior to D30 will be followed up to assess the days in ICU at D30.
- Check if patient is on organ support
- The number of organ failure free days by means of SOFA (arterial blood gas analysis should not be done if not part of standard care at this point).
- Physical Examination of major body systems
- Vital signs (temperature, BP and HR) must be measured and recorded between 6 am to 10 am using the values closest to 8 am (assuming these values are representative of the patient's condition). All vital signs assessments must be made at the same time point when possible.
- Intra-abdominal pressure (IAP) must be measured daily between 6 am to 10 am during ICU stay or complete resolution of elevated pressure
- Days on vasoactive drugs
- Recording of concomitant medications and therapies
- AE reporting
- Patient is invited for a laboratory visit to assess NABs and other D30 assessments on D30.
- Mortality follow-up: For all patients who withdraw from the study prior to D30, mortality will be assessed at D30 and D90 (3 months). **Note:** A time window of +14 days is given for D90 assessment.

In the case of an ongoing AE, appropriate safety evaluations and/or additional tests may be performed at any time when clinically indicated at the discretion of the Investigator, until resolution or D30, whichever is the sooner.

Any ongoing AEs should be followed up to resolution or study D30, whichever is the sooner.

If the patient refuses any of the above assessments or is lost to follow-up, this is noted in the eCRF.

If a patient is lost to follow-up, mortality data will be sought from alternate sources such as the patient's local physician or available national databases, whenever possible.

